9.2.2 Sestamibi evaluation

In patients who had a sestamibi study performed prior to the fluorocholine imaging study, we will use the original dictated report from the sestamibi. This will be done as there may be significant bias in the interpretation of the sestamibi studies if re-interpreted. Identical to the PET data, the study reports, will be used to characterize location (left/right, location with respect to the thyroid, or description of location if atypical). All suspected lesions as well as the single most suspicious lesion will be recorded. The sensitivity from this analysis will be used as our comparator for the FCH PET. For each reader, lesions will be characterized as follows:

1. True positive: Location of the suspected adenoma on sestamibi correlates with location of an abnormal parathyroid at time of surgery. For a patient with multiple hyperplastic glands, only one gland needs to correlate for the patient to count as a true positive.
 - a. For analysis, adenomas described as arising in the mid thyroid bed will be considered correct if located in either the inferior or superior bed.
2. False positive: Location of the suspected adenoma on sestamibi does not agree with location of an abnormal parathyroid at time of surgery.
3. True negative: There are no true negatives as patients with primary hyperparathyroidism have near 100% incidence of hyperplastic adenomas.
4. False negative: No evidence of parathyroid adenoma on sestamibi independent of findings at time of surgery.

The performance of the imaging modalities will be quantified by sensitivity, specificity, positive predictive value and negative predictive value.

Performance will be assessed using surgery as the gold standard with postoperative normalization of calcium as the study endpoint as described above. For this study to have a positive outcome, two of the three FCH PET readers have to have a sensitivity that is 10% greater than that of sestamibi imaging. For statistical analysis we will use the McNemars's test with a p-value of 0.05 for significance. We will also compare the sensitivity of 18F-fluorocholine to the predetermined detection sensitivity of 70%. Again, two of the three FCH PET readers have to have a sensitivity that is 10% greater than 70% (ie 80%). We will also report an interreader variability for the FCH PET reads using a Fleiss's Kappa. The baseline characteristics will be reported as follows: continuous parametric data will be reported as mean

+- standard deviation, continuous non-parametric data as medians with interquartile range. Dichotomous data will be reported as proportions. Patients with missing imaging results or missing data on the primary endpoint will be excluded from the study.

In patients who do not subsequently undergo parathyroidectomy, we will use the dictated reports to determine the detection sensitive for parathyroid adenomas.

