1.1 Background

Primary hyperparathyroidism (PHPT) is a common endocrine disorder, with an incidence of around 45 per 100,000 person years (1). PHPT is characterized by autonomous hypersecretion of parathyroid hormone (PTH) by one or more parathyroid glands, leading to an elevated serum calcium concentration. Hypercalcemia can cause a wide variety of well-described symptoms ranging from constipation to osteoporosis and also increases the risk of mortality resulting from cardiovascular disease (2). Diagnosis is typically established biochemically, with the finding of a relatively elevated serum calcium level with a concomitant inappropriately-elevated PTH level. In over 80% of cases, PHPT is caused by a single parathyroid adenoma. The remainder of other causes includes multigland disease (either multiple adenomas or 4-gland hyperplasia) and very rarely parathyroid carcinoma (3). Surgery is currently the only method of definitive cure as well as the most effective treatment modality overall. Most patients with PHPT are surgical candidates, but particularly if they are symptomatic or younger than 50 years of age (4). In the majority of cases, the method of surgical intervention has shifted over the past 2 decades, evolving from extensive bilateral neck exploration to a more minimally invasive parathyroidectomy (MIP) approach (5). MIP has been made possible by improvements in preoperative imaging studies that are able to accurately identify (localize) the abnormal gland(s), which in turn have allowed surgeons to perform limited, targeted explorations, with its attendant benefits to shorter operative time, lower complication rate, and smaller incision length (2). Most centers including UCSF routinely perform a combination of neck ultrasound and Tc-99m-sestamibi scan (with or without fusion SPECT-CT) for first-time, non-reoperative cases. The diagnostic value of single photon emission computed tomography (SPECT/CT) in predicting the localization of the adenoma has been proven to be the best imaging modality in comparison to normal SPECT, dual-phase planar scintigraphy and subtraction scintigraphy (6-8). However, even SPECT/CT fails to identify the gland in up to 30% of the cases (9). These cases mandate the traditional bilateral neck exploration, with its abovementioned attendant disadvantages compared to MIP.

1.2 18F-fluorocholine for parathyroid adenomas

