7.1.2 Imaging Period

7.1.2.1 Study Procedures (Day 1)

- Administration of 18F-fluorocholine
 - The one-time nominal injected dose will be 4 to 7 mCi containing FCH. Patient shall begin imaging between 20 and 60 minutes after the injection of the radiopharmaceutical.
- Imaging using either PET/CT or PET/MRI
 - Coverage for the scan will extend from the base of the skull to the pulmonary artery. PET acquisition will be for a minimum of 10 minutes per bed position.
 - A dictated report will be made of the imaging findings and be provided to the endocrine surgeons. FCH PET imaging results will be used in conjunction with other imaging modalities, including available ultrasound and sestamibi studies, to direct surgical intervention.

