7.1.3 Long Term Follow-up Procedure

Patients will be followed-up off protocol for up to one year. For patients who subsequently undergo parathyroidectomy, the determination of biochemical cure will proceed per the usual standard of care, including the use of intraoperative PTH (IOPTH) measurements, and calcium and PTH measurements in the postoperative setting at standardized intervals. Biochemical cure will be documented if the 2-4 week postoperative serum calcium and PTH levels drop both in comparison to preoperative values as well as to normal ranges. In addition, the final pathological diagnosis will be recorded for comparison purposes.

8 Reporting and Documentation of Results

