9.1 Statistical Design

We will enroll a total of 140 patients (65 in our initial cohort, on which the sample size estimate is based). The sample size will be based upon comparison to setamibi SPECT (MIBI). Multiple meta-analysis of MIBI SPECT have been performed and demonstrate a sensitivity ranging 79 to 84% for MIBI SPECT (15,16). This detection rate is higher than we see at our institution since we are a referral center for patients who have previously failed parathyroidectomy, where the study has a lower sensitivity. For the purpose of our analysis we will do our sample size assuming a sensitivity of 70%, which mirrors our practice. At an 87% power with an alpha level of 0.05, we estimate that a sample size of 65 patients would be needed, assuming 100% disease prevalence, 70% accuracy of MIBI (sestamibi), an estimated 85% accuracy of FCH PET, and 10% dropout rate.

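### The false-positive rules for both scans count a call at an unexplored site as wrong even in an uncured patient, although the scans being compared help decide where the surgeon looks

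*Combined protocol and SAP*

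**What the plan says.** - Section 7.1.2.1: the FCH findings are reported to the endocrine surgeons, and "FCH PET imaging results will be used in conjunction with other imaging modalities", ultrasound and sestamibi among them where available, to guide the operation.
- Section 1.1 describes the surgical setting in general terms: better preoperative imaging is said to "have allowed surgeons to perform limited, targeted explorations". It adds: "In over 80% of cases, PHPT is caused by a single parathyroid adenoma".
- Section 9.2.2 on sestamibi: "False positive: Location of the suspected adenoma on sestamibi does not agree with location of an abnormal parathyroid at time of surgery". Section 9.2.1 has the same rule for FCH PET. In both, one matching gland is enough for a true positive in multigland disease, and a false negative is a scan with no finding at all.
- Section 7.1.3: "Biochemical cure will be documented if the 2-4 week postoperative serum calcium and PTH levels drop", judged against preoperative values and normal ranges. It also mentions intraoperative PTH.
- Section 9.2.2 names surgery as the gold standard together with postoperative calcium normalization. It does not say how cure or non-cure changes a true-positive or false-positive label.
- Section 9.2.2 on the test for endpoint 1: "For statistical analysis we will use the McNemars's test with a p-value of 0.05 for significance". Success also needs a sensitivity 10% above sestamibi for two of three blinded readers.
- Section 9.2.2 excludes patients with missing primary-endpoint data, without saying whether an unexplored site or an uncured patient counts as missing.

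**The concern.** A surgical reference standard verifies only the sites that were inspected. Here the choice of sites is influenced by the scans being compared. If an operation is limited to one scan's site, an abnormal gland is removed there and the patient is not cured, the other scan's site remains an open question. The rule as written closes that question against the uninspected scan.

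This matters for primary endpoint 1 because McNemar's test uses only discordant pairs. If the two scans mark different glands and both glands are abnormal, both scans should be true positives and the pair should not count. Scoring one of them as a false positive moves the pair into a cell that does count.

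The point concerns operated patients with an unexplored site. It does not concern who gets operated.

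**Working it through.** **1. The plan's own figure.** Section 9.1 states: "At an 87% power with an alpha level of 0.05, we estimate that a sample size of 65 patients would be needed", with "70% accuracy of MIBI (sestamibi), an estimated 85% accuracy of FCH PET, and 10% dropout rate". A one-sample normal approximation with p0 = 0.70, p1 = 0.85, one-sided alpha 0.05 and power 0.87 gives

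n = [(1.645 × √(0.70 × 0.30) + 1.126 × √(0.85 × 0.15)) / 0.15]² ≈ 59.4, so 60, and 60/0.9 = 67.

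That is within 2 of 65. At 59 evaluable patients (65 × 0.9 = 58.5) the power is 86.8%. The stated size is therefore broadly reproducible and is not in dispute here.

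**2. Which patients are affected.** Take an FCH call at site A and a sestamibi call at site B.

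| Explored | Finding | Cured? | FCH | Sestamibi | Is the scoring sound? |
|---|---|---|---|---|---|
| A and B | either | either | by inspection | by inspection | Yes |
| A only | A abnormal | yes | TP | FP | Yes, cure supports it |
| A only | A abnormal | no | TP | FP | B is unverified |
| A only | A normal | no | FP | FP | B is unverified, but no FCH win arises |
| B only | B abnormal | no | FP | TP | A is unverified (mirror image) |

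Rows 3 and 5 create one-scan wins on unverified evidence, in opposite directions.

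**3. Effect per patient.** If a false positive counts as a miss (sensitivity = TP/N), one re-labelled patient moves one scan by 1/59 = 1.7 points. Six patients give 6/59 = 10.2 points, the whole 10-point margin.

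If sensitivity is TP/(TP + FN), as the false-negative definition permits, the effect is smaller. With assumed counts of 41 TP, 6 FP and 12 FN, moving 3 patients from TP to FP changes:
- TP/N from 41/59 = 69.5% to 38/59 = 64.4%
- TP/(TP + FN) from 41/53 = 77.4% to 38/50 = 76.0%

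The plan does not say which denominator applies.

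**4. Effect on the test if all errors ran one way.** Assume that both scans have 70% true sensitivity with independent errors (0.70 × 0.30 = 0.21 in each discordant cell), that false positives count as misses, and that a share u of all patients moves from both correct to FCH-only correct. The cells are then 0.21 + u and 0.21. Ignoring the 10% margin and the two-of-three-reader rule, the asymptotic two-sided McNemar test at 0.05 falsely favours FCH with probability:

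| u | 59 evaluable | 126 evaluable (140 × 0.9) |
|---|---|---|
| 0 | 2.5% | 2.5% |
| 2% | 4.2% | 5.2% |
| 5% | 8.0% | 12.6% |
| 10% | 18.3% | 34.2% |

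The documents give no value for u.

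**5. A gross upper range for u.** Take 20% multigland disease (a ceiling, since section 1.1 says over 80% are single adenomas). Assume that the scans point to different abnormal glands in d = 10% to 30% of those, and that the sestamibi site is unexplored in e = 50% to 100%. Then 0.20 × d × e runs from 0.20 × 0.10 × 0.5 = 1 point to 0.20 × 0.30 × 1.0 = 6 points, or 0.6 to 3.5 patients of 58 (58.5 rounded down).

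This is gross. The values of d and e have no basis in the documents, there is no term for non-cure, nothing is subtracted for unexplored FCH sites, and a false positive is taken as a miss. If unexplored FCH sites are equally frequent, the net shift is about zero.

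**The case against.** A reader might infer that the rule tilts endpoint 1 toward FCH by several points. The documents do not support that:
- The false-positive rules are worded identically for the two scans, and section 7.1.2.1 has sestamibi and ultrasound guiding surgery alongside FCH. Row 5 of the table is as possible as row 3.
- The FCH read that reaches the surgeon is the unblinded clinical one, which section 9.2 keeps out of the primary endpoint. An FCH win needs a blinded reader to name the explored site, and success needs two of three readers.
- Limited exploration is described in section 1.1 as a general trend. The protocol prescribes no operative approach, and intraoperative PTH may prompt further exploration before the operation ends.

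A reader might also infer that the plan disregards cure. It does not: section 9.2.2 names calcium normalization beside the surgical gold standard.

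These arguments remove the claim of direction and size. They do not remove the gap. Identical wording does not ensure that both scans' sites are explored equally often. Blinding the readers does not make the surgical reference independent of the scan they read. And naming cure without linking it to the four categories leaves rows 3 and 5 scored as if every site had been inspected.

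**Conclusion.** The point holds as a verification gap. The plan has no category for an unexplored site in an uncured patient, for either scan, and does not connect the cure data it collects to the scoring. Such patients can turn a concordant pair into a one-scan win in McNemar's test.

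The effect could favour FCH if surgeons give FCH more weight, but neither the direction nor the size of the net bias can be derived from the documents. The number of patients is probably small, since it is limited to uncured patients with an unexplored site. The 1 to 6 point range is a gross upper range under assumed inputs, not an estimate, and the effect shrinks if false positives are left out of the sensitivity denominator. The gap is still worth closing before analysis, because each patient can be worth 1.7 points at 59 evaluable and the data needed are largely in hand.

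**What to change.** 1. Record from the operative note which sites were explored.
2. In sections 9.2.1 and 9.2.2, for both scans alike, score a call at an unexplored site as false positive only when biochemical cure followed removal of glands elsewhere. Otherwise label it unverified.
3. State which definition of cure applies, reconciling section 7.1.3 (calcium and PTH) with section 9.2.2 (calcium only), and say whether an unverified call counts as missing data.
4. Add a sensitivity analysis of endpoint 1 for each reader, with unverified calls scored once as wrong and once as correct, and report their number for each scan. Leave the success criterion unchanged.

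The cost is one data field and one extra analysis. Surgery and patient care are not affected. The FCH difference may come out less favourable in the sensitivity analysis. If few calls are unverified, the same analysis shows that the result is robust.

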Rationale for Study	Based on the promise shown in the preliminary results of these FCH PET pilot studies, we propose to evaluate this modality in a larger, appropriately powered prospective study. Specifically, we propose to conduct a large prospective study comparing the accuracy of US and MIBI with FCH PET (with either low-dose CT or MRI) as first-line imaging modalities in patients with HPT. We believe that this more robust study design will provide more rigorous evidence on the true accuracy and added value of FCH PET for parathyroid localization.
Primary Objective	To investigate the performance (accuracy) of 18F-fluorocholine PET in the detection of hyperfunctioning parathyroid glands in surgical patients with biochemically proven primary hyperparathyroidism.
Study Design	This is a single arm Phase III study evaluating the accuracy of 18F-fluorocholine for the detection of parathyroid adenomas.
Number of patients	140 patients.
Duration of Therapy	Patients will receive a single dose of 18F-Fluorocholine.
Duration of Follow up	Patients will be followed-up off study to determine if they undergo a parathyroidectomy.
Duration of study	The study will reach completion five years from the time the study opens to accrual.
Study Drugs	18F-fluorocholine.
Safety Assessments	Patient reported adverse events during the day of imaging will be recorded.
Efficacy Assessments	The 18F-fluorocholine PET studies will be interpreted by three blinded readers, and the reads will be correlated with pathology at time of parathyroidectomy to determine the accuracy of 18F-fluorocholine PET to detect the location of an abnormal parathyroid adenoma. Additionally, the accuracy of 18F-fluorocholine will be compared to sestamibi when available.

List of Abbreviations

AE	adverse event
CRC	Clinical Research Coordinator
CRF	case report form
CT	computerized tomography
CTCEA	Common Terminology Criteria for Adverse Events
CTMS	Clinical Trial Management System
DSMP	Data and Safety Monitoring Plan
FCH	18F-fluorocholine
FDA	Food and Drug Administration
GCP	Good Clinical Practice
IND	investigational new drug application
IP	investigational product
IRB	Institutional Review Board
IV	intravenous
MRI	magnetic resonance imaging
PET	positron emission tomography
PK	pharmacokinetics
PTH	parathyroid
SD	standard deviation
SPECT	Single photon emission computed tomography

Table of Contents

Protocol Signature Page	2
Abstract	3
List of Abbreviations	4
1 Introduction	7

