2.1 Primary objective

To investigate the performance (accuracy) of 18F-fluorocholine PET in the detection of hyperfunctioning parathyroid glands in surgical patients with biochemically proven primary hyperparathyroidism.

3 Study Endpoints

3.1 Primary endpoint 1

Sensitivity and specificity of 18F-fluorocholine PET for the detection of abnormal parathyroid adenomas confirmed by pathology as compared to sestamibi imaging.

3.2 Primary endpoint 2

Sensitivity and specificity of 18F-fluorocholine PET for the detection of abnormal parathyroid adenomas confirmed by pathology as compared to a predefined threshold.

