9.2 Analyses Plans

At the time of the imaging study, each scan will be interpreted by a nuclear medicine physician, who will be fully cognizant of the clinical, imaging and laboratory data. Focal uptake on choline PET will be reported by location (left/right, location with respect to the thyroid, or description of location if atypical), along with measured SUVmax. These reads will not be used for evaluation of the primary endpoint.

9.2.1 18F-fluorocholine blinded reads

All 18F-fluorocholine imaging data will be anonymized and collected. PET data will be interpreted by three different board certified nuclear medicine readers in a random order at separate reading sessions. Prior to interpretation a training data set using choline PET studies not included in the study will be used to train the readers. Clinical information will not be available to the readers at time of interpretation. Cross sectional imaging from the PET will be available for anatomic correlate, but no other imaging study will be available. Each study will be characterized by location (left/right, location with respect to the thyroid, or description of location if atypical). "Atypical" refers to adenomas that are not in the thyroid bed and would include the mediastinum. All suspected lesions as well as the single most suspicious lesion will be recorded. For example, in the setting of multiple parathyroid adenomas, one lesion will be reported by the readers as most suspicious.

The location of each adenoma that is surgically confirmed will be marked in the identical fashion (left/right, location with respect to the thyroid [ie inferior or superior], or description of location if atypical). For each reader, lesions will be characterized as follows:

1. True positive: Location of the suspected adenoma on FCH PET correlates with location of an abnormal parathyroid at time of surgery. For a patient with multiple hyperplastic glands, only one gland needs to correlate for the patient to count as a true positive.
 - a. For analysis, adenomas described as arising in the mid thyroid bed will be considered correct if located in either the inferior or superior bed.
2. False positive: Location of the suspected adenoma on FCH PET does not agree with location of an abnormal parathyroid at time of surgery.
3. True negative: There are no true negatives as patients with primary hyperparathyroidism have near 100% incidence of hyperplastic adenomas.

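### The reference standard for the primary endpoints is not reconciled across sections, and postoperative calcium cannot serve as the endpoint for scan sensitivity

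*Combined protocol and SAP*

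**What the plan says.** Three descriptions of the reference standard appear.

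- **Pathology.** Section 3.1 concerns "detection of abnormal parathyroid adenomas confirmed by pathology as compared to sestamibi imaging", and section 3.2 concerns "detection of abnormal parathyroid adenomas confirmed by pathology as compared to a predefined threshold". The synopsis agrees: "the reads will be correlated with pathology at time of parathyroidectomy".
- **Location at surgery.** Section 9.2.1 defines a true positive as "Location of the suspected adenoma on FCH PET correlates with location of an abnormal parathyroid at time of surgery". Section 9.2.2 uses the parallel rule for the comparator: "Location of the suspected adenoma on sestamibi correlates with location of an abnormal parathyroid at time of surgery". With several hyperplastic glands, "only one gland needs to correlate for the patient to count as a true positive". These definitions mention neither pathology nor calcium.
- **Calcium.** After those definitions, section 9.2.2 says performance will be assessed using "surgery as the gold standard with postoperative normalization of calcium as the study endpoint", and refers back to an earlier description.

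The only earlier biochemical description is in section 7.1.3, which uses two markers: "Biochemical cure will be documented if the 2-4 week postoperative serum calcium and PTH levels drop both in comparison to preoperative values". That section also records the pathological diagnosis, but only for comparison. Section 3 contains no calcium endpoint.

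On the other outcomes, a positive scan at the wrong site is a false positive. A false negative is a scan showing no adenoma, whatever surgery finds. Section 9.2.2 ends by excluding patients who lack primary-endpoint data.

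**The concern.** No section ranks or combines the three standards, or says how to classify a patient when they disagree. Surgical and laboratory results will be known when reads are classified, so the choice could be made after seeing which rule favours the scan.

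The calcium clause is the serious part. Calcium normalisation measures whether the operation succeeded, whereas sensitivity asks whether the scan pointed to the right place. Section 7.1.2 lets surgeons use FCH PET together with other imaging, so cure does not show that PET was right and persistent disease does not show that it was wrong.

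The clause also blurs the denominator. A patient with full surgical findings but no postoperative calcium is evaluable under 9.2.1, and arguably has missing endpoint data under the calcium wording.

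Endpoint 2 has a fixed bar of 80%, only 5 points below the assumed 85%, so the classification rule could matter there.

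**Working it through.** **1. Where the rules part company**

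| Patient | Location rule (9.2.1, 9.2.2) | Other wording |
|---|---|---|
| Multigland disease, scan matches one gland, calcium stays raised | True positive | Calcium endpoint (9.2.2) not met |
| Gland judged abnormal at the scan site, pathology does not confirm | True positive | Not confirmed under 3.1/3.2 |
| Scan site wrong, gland found elsewhere, calcium normalises | False positive | Calcium endpoint (9.2.2) met |
| Scan site right, calcium normalises, PTH does not | True positive | Met under 9.2.2, not cured under 7.1.3 |

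The first row is foreseeable: section 1.1 puts single adenomas at over 80% of cases, with multigland disease making up most of the rest.

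**2. The plan's own figure.** Section 9.1 gives 65 patients for 87% power, alpha 0.05, 70% against 85%, and 10% dropout. A one-sided one-sample test comes close:

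n = (1.645·√(0.70·0.30) + 1.126·√(0.85·0.15))² / 0.15² = 59.4, so 60.

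With dropout this is 60/0.9 = 67, or 60·1.1 = 66, within 2 of 65. The point here does not rest on an arithmetic error.

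**3. Size, by assumption.** Let f be the share of FCH location hits not upheld by a further criterion. The documents give no value, so 2%, 5% and 10% are assumed. Also assumed: baseline sensitivity is 85% and every baseline non-hit is a negative scan. Evaluable patients are 65·0.9 = 58.5, taken as 58.

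- *Written definitions:* a positive scan that fails the standard is a false positive and leaves TP/(TP+FN). Sensitivity = 0.85(1−f) / [0.85(1−f) + 0.15]. At 10%: 0.765/0.915 = 83.6%.
- *Counted as misses:* these patients stay in the denominator. Sensitivity = 0.85(1−f). At 10%: 76.5%.

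The chance that one reader observes at least 80% is an exact binomial tail. With 58 in the denominator, at least 47 hits are needed (0.8·58 = 46.4). Under the written definitions the denominator is 58 minus a binomial(58, 0.85f) number of false positives, and the tail is averaged over it.

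| f (assumed) | Sensitivity, false positives | Chance ≥80% | Sensitivity, misses | Chance ≥80% |
|---|---|---|---|---|
| 0 | 85.0% | 0.85 | 85.0% | 0.85 |
| 2% | 84.7% | 0.85 | 83.3% | 0.75 |
| 5% | 84.3% | 0.83 | 80.8% | 0.56 |
| 10% | 83.6% | 0.78 | 76.5% | 0.26 |

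At 140·0.9 = 126 evaluable patients, the chances for 2%, 5% and 10% are 0.93, 0.91 and 0.86 in the first case and 0.86, 0.62 and 0.20 in the second, against 0.95 at f = 0.

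**4. Endpoint 1.** If the same f applies to sestamibi at 70%, counting misses shrinks the expected gap from 15.0 points to 0.15·(1−0.10) = 13.5 at 10%. Under the written definitions sestamibi becomes 0.63/(0.63+0.30) = 67.7%, a gap of 83.6 − 67.7 = 15.9 points. The fixed 80% bar is therefore more exposed than the paired comparison.

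**The case against.** The strongest reply is that the plan has one operational rule, stated in parallel for both scans with its own multigland provision. Surgery locates the gland and pathology examines the same tissue, so those two standards form a sequence. The calcium clause itself names surgery as the gold standard and never says that a patient whose calcium stays raised ceases to be a true positive. The pilot description in 1.3 uses biochemical cure as corroboration of the surgical finding.

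Much of this stands. A reader might infer three mutually exclusive standards, but the documents do not go that far: surgery and pathology are compatible, though the combined rule is nowhere written. A reader might also infer that a few reclassified patients would decide the trial, with the chance of reaching 80% falling to 0.26. That needs non-upheld hits to be counted as misses, whereas the written definitions make them false positives.

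The reply does not rescue the calcium clause. It calls calcium the study endpoint, points back to a description that does not exist in that form, and can disagree with the location rule in both directions.

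**Conclusion.** The point holds as a conflict in the text: the primary reference standard is not reconciled, and calcium normalisation is named as an endpoint that cannot measure scan sensitivity. It should be corrected before any reads are classified.

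The documents do not fix its size. For assumed discordance of 2% to 10%, the effect on endpoint 2 is small to moderate under the written definitions (sensitivity 84.7% to 83.6%; chance of at least 80% from 0.85 to 0.78 at 58 patients). It is large only if those patients are kept as misses (83.3% to 76.5%; 0.75 to 0.26).

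These figures rest on the assumed shares, on all baseline non-hits being negative scans, and on sensitivity meaning TP/(TP+FN), a formula the plan does not write out. They are for one reader. The two-of-three rule is not modelled, and a change of reference standard would affect all three readers together.

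**What to change.** In section 9.2:

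1. State one per-patient classification rule for both primary endpoints and both scans: location match with an abnormal gland at surgery, confirmed by pathology. Write out the sensitivity formula and say what happens when surgery and pathology disagree.
2. Remove the words that make calcium the study endpoint. Report biochemical cure as a pre-specified supportive analysis, for example restricted to patients with documented cure. Do not charge non-normalisation to the scan as a miss, since that would blame the image for an incomplete operation.
3. State which missing component (surgical location, pathology or postoperative laboratory values) makes a patient non-evaluable for the primary analysis.
4. Reconcile the calcium wording in 9.2.2 with the calcium-and-PTH wording in 7.1.3.

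The cost is protocol wording and one supportive table. Surgical location, pathology and postoperative values are already planned for collection.
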